#### D. APPROACH

**D.1. Two studies, WIN and ongoing HAP**, motivate, inform, and support PAI's likelihood of success. These and other studies demonstrate our ability to recruit patients from low income urban neighborhoods with moderate or severe asthma and follow them for significant periods of time. All pertain to the patient-MD relationship beginning with a study of adherence which the IOM and our studies found to be a measure of the success of the patient-physician relationship.

**D.1.1. WIN Study: "Individualized Interventions to Improve Adherence in Asthma" (R01 HL073932; [name], PI),** a randomized controlled trial (RCT), compared problem-solving (PS) to asthma education (AE) to improve inhaled steroid adherence and asthma outcomes in adults with moderate or severe asthma recruited from clinics serving low-income urban neighborhoods. PS involves identifying specific barriers to adherence, proposing and weighing solutions, trying the best, assessing, and revising. Adherence was monitored electronically. 333 adults (English- or Spanish-speaking) were randomized: 49 $\pm$ 14 years, 72% female, 68% African American, 7% Latino, mean FEV1 66% $\pm$ 19%, 52% with ED visits, 31% with hospitalizations for asthma in the prior year. Comorbidities were common: hypertension in 52%, diabetes in 22%, mean BMI 33 $\pm$ 9. In an intention to treat (ITT) analysis, there was no difference between groups with respect to overall change in any outcome ( $p>0.20$ ). Mean adherence was 61%  $\pm$  27%. Both groups changed similarly from baseline: adherence declined overall by 12% but asthma control, asthma-related quality of life (AQOL), and FEV1 improved overall by 15%, 18%, and 6% respectively. ED visits and hospitalizations did not significantly decrease. While PS was not better than AE, monitoring adherence with provision of medications and attention to patients given to both groups was associated with improvement in some asthma outcomes. Electronic monitoring is not a real-world intervention. Changes in inhaler formulation will make current monitors obsolete. Thus, monitoring is unlikely to be a feasible or cost-effective intervention.

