**Table 1. Data Collection for Specific and Secondary Aims**

Measure	Visit 1 Baseline Randomization	Visit 2 Week 12	Visit 3 Week 24	Visit 4 Week 36	Visit 5 Week 48
Mediators					
Self-efficacy	x	x	x	x	x
Appointment keeping	x	x	x	x	x
Adherence	x	x	x	x	x
Satisfaction with communication	x	x	x	x	x
Navigating ability	x	x	x	x	x
Moderators					
Educational attainment	x				
Baseline health literacy (ANQ, S-TOFHLA)	x				
Socio-demographics	x				
Comorbidities*					
Community factors (ECV)	x				
Affective State: Anxiety/Depression	x				
Clinician characteristics	x				
Participant Outcomes					
Asthma Control	x	x	x	x	x
Prednisone bursts, ED, hospitalizations	x	x	x	x	x
Asthma-Related Quality of Life (AQOL)	x	x	x	x	x
Spirometry (FEV1, FVC)	x	x	x	x	x

\*Comorbidities include diabetes, hypertension, obesity, cancer, smoking history, and other conditions as reported by participant and verified in the medical record. ANQ= Asthma Numeracy Questionnaire, S-TOFHLA= Short Test of Functional Health Literacy in Adults, ECV= Exposure to community violence.

**D.3. Subjects: Inclusion criteria** for 300 subjects (1-5 also of the HAP Study) are: 1)  $\geq 18$  years of age, 2) physician's diagnosis of asthma, 3) prescribed an inhaled-steroid-containing medication for asthma (ensuring the patient is believed to have moderate or severe reversible airways obstruction by their physician), 4) moderate or severe persistent asthma according to the NHLBI Guidelines, 5) evidence of reversible airflow obstruction: (a) forced expiratory volume in 1 second (FEV1)  $< 80\%$  predicted at the time of screening or within the 3 years prior to this screening, and (b) improvement with bronchodilator: either (i) an increase of  $\geq 15\%$  and 200ml in FEV1 with asthma treatment over the previous 3 years or (ii) after 4 puffs of albuterol by MDI (or 2.5 mg by nebulizer), an increase in FEV1 or FVC  $\geq 12\%$  and 200 ml in FEV1 within 30 minutes, and 6) at least one appointment scheduled with the asthma physician during the 1st 6 months of participation.

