**Specific Aim 3 (To estimate the incremental costs and incremental cost-effectiveness (ICE) of PA):** ICE will be assessed by comparing the incremental cost of PA (including both intervention costs, as well as costs of care) relative to UC per outcome, e.g. cost per day asthma control or avoided ED, hospitalization. The ICE will be determined based on differences in direct costs (payer perspective) and also including indirect

costs (societal perspective) and will be calculated based on differences in mean costs for the UC group from those in the PA group, divided by the mean difference in outcomes (asthma control, prednisone bursts, ED visits, hospitalizations, etc.). We also will calculate the incremental cost per quality adjusted life year as estimated from the AQOL. We will estimate statistical error and construct confidence intervals using bootstrap procedures for the incremental cost difference and the incremental cost-effectiveness ratio (ICER).

**Exploratory Aim (Post-study focus groups of providers):** Audio records and notes will be coded into categories emerging from the data by independent coders ([name], [name], [name]) who will achieve inter-coder reliability. Using the Grounded Theory approach, we will then analyze the agreed upon categories, and place them into themes emerging from discussions.

**D.10. Sample size:** We will enroll 300 adults (150 per intervention group). The primary outcome (Aim 1) is asthma control at Visit 3 (6 months) and Visit 5 (12 months). While a clinically meaningful difference in asthma control within-individual is 0.5, we expect the average difference across groups to be smaller. The WIN Study demonstrated a small difference in mean change of  $0.2 \pm 1.1$  in asthma control across intervention groups at Visit 8 (6 months). The effect was neither clinically nor statistically significant. A difference in mean change of 0.32 in asthma control was found in a study with a different focus, but the effect was not statistically significant, probably due to the small sample size.

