**Specific Aim 1:** The power analysis is based on the 2-sample t-test with adjustments for 3 or 5 repeated measures per participant. The adjustment for clustering by patient multiplies the estimated sample size under simple random sampling by a design effect,  $d=1+\rho(n-1)$ , where  $n$ =average number of visits per patient, and  $\rho$  is the patient intraclass correlation. We apply a conservative intraclass correlation of 0.30. The power analysis also takes into consideration the following factors: 1) 18% drop-out as observed in WIN; 2) adjusted 2-sided significance level of 0.025; and 3) 80% power. With these factors, the study is powered to observe a standardized effect of 0.29 and 0.32 difference in mean change in asthma control across intervention groups at 6 months and 12 months, respectively. **Specific Aim 2:** The power analysis examines the intervention effect on 5 asthma outcome measures at 6 and 12 months. Using the same assumptions but with 2-sided  $\alpha=0.005$  to conservatively adjust for multiple comparisons, we will have 80% power to detect a standardized effect of 0.34 and 0.31 between groups at 6 months and 12 months, respectively. **Specific Aim 3:** Power for the economic analysis (costs have greater variability than clinical outcomes) is 81% based on the same effect size, 2-sided  $\alpha$  of 0.05, an effect-cost correlation of -0.1, a difference in cost of \$500 and a willingness to pay (WTP) threshold of \$2500 per year of improved adherence or avoided hospitalization. An increase in the WTP to \$3000 results in 98% power. Thus, the sample size will provide sufficient statistical power for assessment of both clinical and economic evaluations (which requires detecting both effect and cost differences).

**D.11. Data Management:** The Clinical Research Computing Unit will collaborate to finalize CRFs, construct the database, protect its security, perform data entry, review, query and update data; assist with preparation of DSMB reports, and collaborate with biostatisticians as it has for HAP and WIN studies.

**D.12. The Data Safety Monitoring Board** (see Human Subjects) will meet at study start, year 2, and year 5. At these and every 6 months the DSMB will review reports of accrual, baseline comparability between PA and UC groups, adverse events, safety concerns, data quality, maintenance of confidentiality and recommend study modifications and whether the study can continue.

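### Aim 3 does not pre-specify adjustment of incremental cost for the utilization collected at Visit 1, nor say which effect estimate forms the denominator, so precision available from data already collected is left unused

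*Combined protocol and SAP*

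**What the plan says.** The Specific Aim 3 paragraph of D.9 describes one estimator. The ratio is "calculated based on differences in mean costs for the UC group from those in the PA group", and this is "divided by the mean difference in outcomes". On uncertainty it says: "We will estimate statistical error and construct confidence intervals using bootstrap procedures". No baseline covariate is named for either part of the ratio.

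Table 1 has a row for "Prednisone bursts, ED, hospitalizations" and a row for asthma control. Both are marked in the column "Visit 1 Baseline Randomization" as well as at Visits 2 to 5. The look-back period for the Visit 1 utilization counts is not stated.

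Three other statements bear on the point:

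- D.2.1 stratifies randomization by practice only.
- The opening of D.9 enters site as a fixed effect throughout. It also says that variables found unbalanced at baseline will be handled as confounders in the intention-to-treat, mediator and moderator analyses. The intention-to-treat contrasts are described there for Aims 1 and 2.
- D.9 fits random-effects models for Aims 1 and 2 in which the treatment-by-visit term is the effect on change from baseline. They are linear for continuous outcomes and log-linear for counts.

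**The concern.** Cost is likely to be the noisiest quantity in this trial. D.10 itself notes that "costs have greater variability than clinical outcomes". Past heavy use of acute care can be expected to predict later cost, so a covariate measured before randomization could remove part of that noise at no extra data cost. The Aim 3 text does not take it up.

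The general rules in D.9 do not fill the gap. Site is not prior utilization. The imbalance rule is not worded to reach the economic analysis. Even if it did, it would choose covariates after the baseline data had been seen, and it would give no precision gain when the arms happened to look balanced. Modelling change from baseline cannot help the numerator either, because D.8.4 describes no pre-randomization cost.

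The denominator is open too. For asthma control, the linear model of Aim 1 yields a mean difference that could be used directly. For ED visits, hospitalizations and prednisone bursts, the log-linear models yield log rate ratios, whereas the ratio needs a difference in mean counts. No step connects the two.

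**Working it through.** **The plan's own figure.** D.10 gives 81% power for Aim 3 at a willingness to pay of $2500 and 98% at $3000, with a cost difference of $500, an effect-cost correlation of -0.1 and two-sided alpha of 0.05. It gives no SD of cost, no SD of the economic effect and no sign for the $500, so the 81% cannot be reproduced and no cost SD can be backed out of it. I tried net benefit, with mean difference W·dE − dC and SD = √(sdC² + W²·sdE² − 2·W·ρ·sdC·sdE), taking sdE = 1 and dE = 0.29 to 0.32 from Aim 1:

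- $500 dearer: even with sdC = 0 and 150 per arm, dE = 0.29 gives (725 − 500)/(2500 × √(2/150)) = 225/288.7 = 0.78, which is 12% power. dE = 0.32 gives 300/288.7 = 1.04, which is 18%.
- $500 cheaper: sdC of about $2,050 to $2,840 (across 123 and 150 per arm) gives 81% at $2500, but then only 81% to 83% at $3000, not 98%.

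The size of the present point therefore has to rest on assumed values.

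**Precision.** Let r be the correlation of the Visit 1 covariates with follow-up cost. Adjustment multiplies the variance of the arm difference by 1 − r² and the SE by √(1 − r²). The documents do not give r; 0.2 to 0.5 is assumed. The unadjusted sample with the same precision is 150/(1 − r²) per arm. The last three columns give the 95% half-width of incremental cost, 1.96 × SD × √(2/150) × √(1 − r²), for assumed cost SDs.

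| r | Variance removed | SE factor | Equivalent n per arm | SD $2000 | SD $5000 | SD $10000 |
|---|---|---|---|---|---|---|
| 0 | 0% | 1.000 | 150 | $453 | $1132 | $2263 |
| 0.2 | 4% | 0.980 | 156 | $443 | $1109 | $2217 |
| 0.3 | 9% | 0.954 | 165 | $432 | $1079 | $2159 |
| 0.4 | 16% | 0.917 | 179 | $415 | $1037 | $2074 |
| 0.5 | 25% | 0.866 | 200 | $392 | $980 | $1960 |

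The SE falls by 2.0%, 4.6%, 8.3% and 13.4%. If the stated 81% is taken at face value and the reduction is applied to the whole net-benefit SD, power is Φ((1.960 + 0.878)/√(1 − r²) − 1.960): 82.5%, 84.5%, 87.2% and 90.6%. These are illustrative, because the 81% itself does not reproduce. The gain is smaller if baseline explains only the cost part of net benefit.

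**Chance imbalance.** D.1.1 reports for the earlier WIN cohort "52% with ED visits, 31% with hospitalizations for asthma in the prior year". For 31% and 150 per arm, the SE of the difference between arms is √(2 × 0.31 × 0.69/150) = 0.0534, so the 95% range is ±10.5 points and a gap of 10 points or more has probability 6%. After 18% drop-out (150 × 0.82 = 123 per arm) the SE is 0.0590 and the probability 9%. For the 52% with ED visits the probabilities are 8% and 12%. These figures ignore stratification by practice and assume that WIN's prior-year window resembles the Visit 1 window here.

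**The case against.** The strongest reply is that a difference in arithmetic mean costs with bootstrap intervals is a recognised and valid estimator. That stands: adjustment buys precision, not validity.

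Three stronger readings are tempting and should not be made.

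- A reader might infer that Aim 3 compares plain arm means with nothing else in the model. D.9 puts site in all analyses, and read literally that includes Aim 3, although its Aim 3 paragraph describes no regression to carry the site term.
- A reader might infer that the denominator is unadjusted and therefore conflicts with the effect reported for Aims 1 and 2. The text is silent on this. Nothing rules out using the Aim 1 and 2 estimates, so it is an ambiguity and not a stated inconsistency.
- A reader might infer that an excess of heavy users in one arm would bias incremental cost by some dollar amount. Under randomization it does not. Such imbalance is ordinary sampling error, and the bootstrap interval already carries it. Putting a dollar value on it would also need a unit cost and an admission rate that the documents do not give.

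It is also fair that total cost under D.8.4 includes advocate time, drugs, office visits and, from the societal perspective, productivity. Baseline counts of acute events may predict these only weakly, which would put r near the lower end of the range. Finally, costs are skewed, so a few heavy users may influence a regression; the choice of model has to be written down and not left open.

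**Conclusion.** The point holds as a gap in pre-specification. Aim 3 names no adjustment for Visit 1 utilization, the imbalance rule in D.9 does not supply it, and the source of the denominator is unstated, with no route from the log-linear count models to a mean difference. Neither the unadjusted estimate nor its interval is invalid; the loss is precision and exposure to the imbalance that happens to occur.

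The size cannot be taken from the documents. For an assumed correlation of 0.2 to 0.5, the SE of incremental cost falls by about 2% to 13%, equivalent to 156 to 200 per arm unadjusted in place of 150. At the low end this is negligible; at the high end it is worth having in a Specific Aim, particularly as the data are already being collected.

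**What to change.** In the Aim 3 paragraph of D.9, pre-specify:

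1. Linear regression of cost on arm, site and Visit 1 utilization (ED visits, hospitalizations, prednisone bursts), with the arm coefficient as the incremental cost.
2. Linear regression of each effect, on its mean-difference scale, on the same terms plus baseline ACQ, with the arm coefficient as the denominator. State how this relates to the Aim 1 and 2 estimates, especially for counts.
3. Bootstrap resampling within site and arm, with both regressions refitted in every sample. With 10 sites and 2 arms the cells average 300/20 = 15 participants, and resampling within cells of 15 understates variance by a factor of about 14/15. Small sites should be grouped for resampling, or the variance rescaled.
4. The unadjusted difference reported alongside.
5. The look-back period for Visit 1 utilization, and whether the site and imbalance rules of D.9 apply to Aim 3.

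The cost is a few lines of plan and a little more analysis work, with no new data. The downside is that skewed costs make the adjusted estimate somewhat model-dependent; the unadjusted result alongside guards against that.

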**Aims 1 & 2 (To assess whether PAI improves asthma control and other asthma outcomes):** The ITT effect of PA relative to UC on change in asthma control and other asthma outcomes since baseline at 6 months will be assessed with estimation and testing of the treatment-6 month visit interaction in the linear RE model (described above) with asthma control as the dependent variable. In addition, the treatment-12 month interaction will be tested and estimated to assess if the ITT effect is retained after the PA intervention ends.

**Secondary Aim 1 (Mediators):** The mediation analysis will follow the 4-step regression approach for testing mediated effects of Holmbeck. First, we will examine the association between PAI and mediators (D.8.2) by fitting separate longitudinal RE models with each mediator as the dependent variable. These models will test the effects of the PAI relative to the UC group with respect to change since baseline at each follow-up visit for the potential mediators. Second we examine the association between the PAI and asthma control as described in Aim 1. Third, we will assess the relationship between the mediators and asthma control by fitting separate longitudinal RE models with the mediators (D.8.2) as the independent variables and asthma control as the dependent variable. Finally, the mediators with significant effects at steps 1 and 3 will be included as a lagged time-varying covariate in the ITT linear RE model for asthma control in Aim 1. Mediators of the PAI will be assessed by comparing the randomization (intervention) effect estimate with and without the potential mediator in the model. A reduction of at least 15% in the treatment-visit interaction parameters at 6 and 12 months due to the inclusion of the mediator in the model will be the criteria for a significant mediator.

**Secondary Aim 2: Moderators** of the intervention (D.8.3) will be tested and estimated with 3- and 2-way interactions among the treatment factor, potential moderator, and visit factor in the ITT model in Aim 1. Similarly, moderators of the mediating relationship will be assessed with 3- and 2-way interactions among the treatment factor, mediator, potential moderator, and visit factor in the mediation model in Secondary Aim 1.

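### The Aim 1 and Aim 2 levels in D.10 are Bonferroni-sized and D.9 names no multiplicity procedure; specifying Holm would keep the same error control and gain power when two or more effects are real

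*Combined protocol and SAP*

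**What the plan says.** D.10 sets the Aim 1 target at two time points: "The primary outcome (Aim 1) is asthma control at Visit 3 (6 months) and Visit 5 (12 months"). Among the factors in the Aim 1 power analysis it lists an "adjusted 2-sided significance level of 0.025". For Aim 2, "The power analysis examines the intervention effect on 5 asthma outcome measures at 6 and 12 months", at two-sided 0.005, a level chosen "to conservatively adjust for multiple comparisons".

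D.9, under Aims 1 & 2, takes the treatment-by-visit interaction at 6 months as the ITT effect and adds that "the treatment-12 month interaction will be tested and estimated to assess if the ITT effect is retained after the PA intervention ends". Neither that paragraph nor the rest of D.9 gives a significance level for these tests, defines a family of hypotheses, or names a multiplicity procedure. Neither Bonferroni nor Holm is mentioned anywhere in the document.

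**The concern.** The two levels in D.10 are exactly what Bonferroni gives for families of two and ten tests. Read together with D.9, the natural reading is that each p-value will be compared with a fixed 0.025 or 0.005.

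That is more conservative than it needs to be. Once one hypothesis in a family has been rejected, the others no longer need the full penalty. The loss falls mainly on claims that need more than one rejection, and Aim 1 makes such a claim: improvement at 6 months, and a difference that persists to 12 months. Take p = 0.010 at 6 months and p = 0.040 at 12 months. Fixed levels of 0.025 leave the 12-month effect unproven. Holm rejects both, with the same 5% control.

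The silence of D.9 matters in its own right. A procedure chosen after seeing a 12-month p-value between 0.025 and 0.05 would not be credible.

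**Working it through.** **Inputs from D.10.** "We will enroll 300 adults (150 per intervention group"); "18% drop-out as observed in WIN", which leaves 150 × 0.82 = 123 per arm; "adjustments for 3 or 5 repeated measures per participant"; intraclass correlation 0.30; 80% power.

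**The levels.** Aim 1: 0.05/2 = 0.025. Aim 2: 5 outcomes × 2 times = 10 tests, 0.05/10 = 0.005. Both agree with D.10.

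**The detectable effects.** Effective n per arm = 123 × m / [1 + 0.30(m − 1)], with m visits:
- 6 months (m = 3): 123 × 3/1.6 = 230.6
- 12 months (m = 5): 123 × 5/2.2 = 279.5

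Detectable effect = (z for alpha + z for power) × √(2/n). The z sum is 2.241 + 0.842 = 3.083 at 0.025 and 2.807 + 0.842 = 3.649 at 0.005.

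| | 6 months: computed (stated) | 12 months: computed (stated) |
|---|---|---|
| Aim 1, 0.025 | 0.287 (0.29) | 0.261 (0.32) |
| Aim 2, 0.005 | 0.340 (0.34) | 0.309 (0.31) |

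Three of the four reproduce. The Aim 1 figure at 12 months does not: under these inputs, power at 0.32 is about 94%. That is a separate matter, but it means that 80% power at 12 months is taken below as D.10's planning target and not as a confirmed value.

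**Holm for Aim 1.** Compare the smaller p-value with 0.025. If it is rejected, compare the other with 0.05.

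Hand check with independent tests, each with 80% power at 0.025 (noncentrality 3.083):
- Power of one test at 0.05: Φ(3.083 − 1.960) = 0.869.
- Fixed levels, both rejected: 0.80² = 0.64.
- Holm, both rejected: both p-values below 0.05, except when both lie between 0.025 and 0.05. This is 0.869² − (0.869 − 0.80)² = 0.755 − 0.005 = 0.75.

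Simulation with correlated normal test statistics. The documents do not give the correlation; 0.3 to 0.65 is assumed.

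| True effects | Quantity | Fixed 0.025 | Holm |
|---|---|---|---|
| 80% power at both times | both rejected | 67-71% | 77-79% |
| 80% power at both times | each time point | 80% | 84-85% |
| 80% power at both times | at least one rejected | 89-93% | 89-93% |
| 12-month effect half as large | both rejected | 22-24% | 31-33% |
| 12-month effect half as large | 6 months | 80% | 80.3-81.1% |
| 6-month effect only | 6 months | 80% | gain about 0.2 points |

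With no true effect, the chance of any rejection is the same under both methods and below 5% (4.4-4.9%).

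**Holm for Aim 2.** Thresholds 0.05/10 = 0.005, 0.05/9 = 0.0056, and so on up to 0.05. With each real effect at 80% power at 0.005 and assumed correlation 0.3-0.5, average power becomes about 82% with four real effects, 84% with six and 90-91% with ten. With one real effect the gain is below 0.1 point.

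**The case against.** **The plan does not prescribe Bonferroni.** A reader might infer that it does. The levels appear only as power-planning inputs in D.10, and 0.05/m is also Holm's first step, so they do not exclude a Holm analysis. This stands. What the documents support is that the levels are Bonferroni-sized and that D.9 says nothing about how they will be applied.

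**Fixed levels are not an error.** They control false positives, and for Aim 2 the plan discloses that it is being conservative. This stands: no bias or inflated error rate is shown.

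**Holm is not better in every respect.** A reader might infer more power always, at no price. Power for at least one rejection is identical, and the gain nearly vanishes when a single effect is real. There is also a reporting cost. Any Aim 1 result that Holm adds has p between 0.025 and 0.05, so its Bonferroni-adjusted interval includes zero. D.9 promises estimation as well as testing, so wanting tests and intervals to agree is a legitimate preference. This stands as a cost to be declared.

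**Other procedures suit Aim 1.** The order in D.9 would fit a fixed sequence. If one claim required both time points, each could be tested at 0.05. These are different choices with their own trade-offs, and they do not make fixed Bonferroni levels preferable to Holm.

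**The gains rest on assumptions.** The correlation is not in the documents. Equal power at both times may also be optimistic, because the intervention stops at 6 months. The half-size scenario addresses this: the joint gain is still about 9 points, from a much lower base.

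**Conclusion.** The point holds as a cheap improvement in efficiency and pre-specification, not as a flaw in validity. The only levels in the documents are Bonferroni-sized and D.9 names no procedure. Holm gives the same family-wise control and never rejects less. For Aim 1 it adds about 8 to 10 percentage points of power to show both the 6-month and the 12-month effect when each has 80% power, and about 9 points when the 12-month effect is half as large. For Aim 2, average power rises by about 2 to 11 points with four to ten real effects. These sizes depend on the assumed correlations (0.3-0.65 for Aim 1, 0.3-0.5 for Aim 2) and on 80% power for each full-size effect. They do not carry over to the case of a single real effect, where there is almost nothing to gain.

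**What to change.** Add to D.9, before outcome data are unblinded:
- The 6- and 12-month tests of asthma control form one family, and the ten Aim 2 tests another.
- Each family is tested by Holm at overall two-sided 0.05: 0.025 then 0.05 for Aim 1; 0.005, 0.0056 and so on up to 0.05 for Aim 2.
- Unadjusted 95% intervals are reported alongside Bonferroni-adjusted ones. Where an Aim 1 result is rejected only at the second step, the report states that its Bonferroni-adjusted interval includes zero.

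In D.10, label the detectable effects as single-test, first-step statements. Holm does not change them or the 300 participants.

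The cost is a few lines of wording and the imperfect match between tests and intervals. If the sponsor prefers fixed levels for the sake of that match, D.9 should still name the procedure and the families.

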The analysis will be based on random effects (RE) models applied to baseline and all follow-up visits at which outcome data are collected. The RE will be included to account for correlated and missing data. Separate time effects and time-treatment interactions will be specified for each follow-up visit, such that the treatment-time interaction for a particular visit will be the ITT effect on change since baseline. The RE models will be linear, logistic, and log-linear for continuous, binary, and count outcomes, respectively. Similar RE models will be employed for assessment of mediation and moderation in Secondary Aims 1 and 2.

**Data description, screening, and reorganization:** We will screen data for quality and integrity as proposed by Altman. For all variables we will determine measures of central tendency: mean and standard deviation for continuous variables, median and range for categorical variables. We will examine frequency distribution graphically (histograms, scatter plots) for all variables. Specific concerns will be directed to understanding the pattern of missing values, isolating outliers, confirming the homoscedasticity of observation groups, verifying the coding consistency, examining adherence to normality for variables anticipated to be so, and locating normalizing transformations for continuous variables intended to be investigated as such. For the tools we developed, we will examine internal consistency using Cronbach's  $\alpha$ .

**Addressing the impact of site on each outcome:** First, we will pool participants across sites, assuming no site effect, using logistic and regression modeling to isolate the relationship between outcome and exposure and other demographics. We have stratified randomization to analyze the effect of site. We have amplified the sample size (D.10) to have a large enough sample to conduct this analysis. As a secondary analysis, we will examine treatment-site interactions. In the presence of statistically significant interactions, we will present separate estimates of treatment effects for each site. In the case of statistically, but clinically marginally significant interactions, we will present main effect estimates of treatment effect but with interactions in the model using -1, 0, 1 dummy coding for site, so that the main effects' estimates will be for the average site.

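### D.10's 80% power is computed for an effect averaged over 3 or 5 visits, but D.9 tests change at single visits; and Aim 1's 12-month 0.32 contradicts Aim 2's 0.31

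*Combined protocol and SAP*

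**What the plan says.** Section D.10 enrols 150 per arm and names asthma control at Visit 3 (6 months) and Visit 5 (12 months) as the primary outcome. It describes the method thus: "The power analysis is based on the 2-sample t-test with adjustments for 3 or 5 repeated measures per participant". The adjustment is a design effect of 1 + rho(n − 1) with rho = 0.30. The other inputs are "18% drop-out as observed in WIN", a two-sided alpha of 0.025 and 80% power. For Aim 1 it concludes that "the study is powered to observe a standardized effect of 0.29 and 0.32 difference in mean change in asthma control across intervention groups", with the two figures assigned to 6 and 12 months in that order. Aim 2 begins "Using the same assumptions but with 2-sided" alpha of 0.005, and concludes that "we will have 80% power to detect a standardized effect of 0.34 and 0.31 between groups at 6 months and 12 months, respectively".

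Section D.9 fits random effects models with separate treatment effects at each follow-up visit, so that "the treatment-time interaction for a particular visit will be the ITT effect on change since baseline". Aims 1 and 2 are assessed by "estimation and testing of the treatment-6 month visit interaction in the linear RE model". For durability, "the treatment-12 month interaction will be tested and estimated to assess if the ITT effect is retained after the PA intervention ends". Neither section plans a test of a treatment effect averaged over visits for these aims.

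**The concern.** Averaging several correlated measurements reduces variance, so a calculation that credits 3 or 5 visits gives smaller detectable effects than a test of change at one visit. If D.10 credits those visits and D.9 does not use them, the stated 80% is not the power of the planned test.

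The four figures also look inconsistent with each other. At 12 months the looser alpha is paired with the larger detectable effect, although everything else is said to be equal.

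These are the only power figures given for the primary outcome and for Aim 2. If they are too favourable, a null result could be misread as evidence that an effect of the stated size is absent.

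**Working it through.** **Inputs, all from D.10.** 150 × (1 − 0.18) = 123 per arm; rho = 0.30; n = 3 measures by 6 months and 5 by 12 months (Visits 1–3 and 1–5 in Table 1, so baseline is counted).

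Sums of normal quantiles:
- alpha 0.025: 2.2414 + 0.8416 = 3.083
- alpha 0.005: 2.8070 + 0.8416 = 3.649

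√(2/123) = 0.1275.

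**Step 1: reproduce the plan.** For a mean over n visits, the detectable effect is (z sum) × 0.1275 × √([1 + 0.30(n − 1)]/n). The last factor is √(1.6/3) = 0.730 for n = 3 and √(2.2/5) = 0.663 for n = 5.

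| Aim, time | alpha | n | Formula gives | D.10 states |
|---|---|---|---|---|
| 1, 6 months | 0.025 | 3 | 0.287 | 0.29 |
| 1, 12 months | 0.025 | 5 | 0.261 | 0.32 |
| 2, 6 months | 0.005 | 3 | 0.340 | 0.34 |
| 2, 12 months | 0.005 | 5 | 0.309 | 0.31 |

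Three of four match to two decimals. Ignoring drop-out, dividing by 1.18, or dividing participants by the design effect without crediting visits all fit worse. D.10 does not use the word averaging; it is inferred from these matches.

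**Step 2: the 12-month pair.** At 0.32 and alpha 0.025 the same formula gives 94% power, not 80%. The figure that belongs there is 0.26.

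**Step 3: the contrast in D.9.** With equal correlation rho between visits and outcome variance 1, the difference between arms in change from baseline at one visit has variance (per-arm units) 2 × 2(1 − 0.30) = 2.80. With a separate treatment effect at every visit and complete data, this is 2.80 whether 2, 3 or 5 visits are modelled; the extra visits add nothing.

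Detectable effects at 80% power with 123 per arm:
- In SDs of change: 3.083 × 0.1275 = 0.393 (Aim 1) and 3.649 × 0.1275 = 0.465 (Aim 2).
- In outcome SDs, multiplying by √(2 × 0.70) = 1.183: 0.465 and 0.551.

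**Step 4: power at the stated effects.** D.10 does not say which SD standardises the effect, so each cell gives SD of change / outcome SD at rho 0.30. The Aim 2 columns apply to continuous outcomes only.

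| Scenario | Aim 1, 6 m (0.29) | Aim 1, 12 m (0.32) | Aim 2, 6 m (0.34) | Aim 2, 12 m (0.31) |
|---|---|---|---|---|
| 123 per arm | 51% / 37% | 61% / 45% | 44% / 29% | 35% / 23% |
| Linear loss to 18%, all 150 modelled | 58% / 43% | 64% / 48% | 52% / 35% | 39% / 25% |
| No drop-out | 61% / 45% | 70% / 54% | 55% / 38% | 45% / 30% |
| Baseline means constrained equal, 123 per arm | 72% / 56% | 81% / 65% | 69% / 50% | 58% / 40% |

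The linear-loss row has 136.5 per arm observed at 6 months and 123 at 12 months (standard errors 0.141 and 0.145 outcome SD). The last row uses variance 2(1 − 0.09) = 1.82 in place of 2.80; D.9 does not state that constraint. A simulation of 20,000 trials with 123 per arm agreed with the first row to within about one percentage point.

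**The case against.** The mismatch itself is hard to dispute; the serious objections concern its size and the reading of 0.32.

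- **0.32 may be in raw units.** D.10 quotes a WIN spread of 1.1, and 0.29 × 1.1 = 0.319, so 0.32 could be the ACQ-point equivalent of 0.29. That would make the fault a wording error, remove the 0.32 power figures above, and point to SD-of-change scaling. But the sentence assigns the two figures to 6 and 12 months. On this reading that assignment is wrong and Aim 1 has no 12-month figure. The number needs replacing either way.
- **123 per arm is a floor at 6 months.** D.9 keeps all randomised participants in the model, and some who leave will do so after Visit 3. This is fair: linear loss raises the primary figure to 58% / 43%, still well short of 80%.
- **The visit correlation matters.** On outcome-SD scaling with 123 per arm, power at 0.29 is 51% at an assumed correlation of 0.5 and 76% at 0.7. It reaches 80% at about 0.73, or at about 0.7 with 136.5 per arm. The documents give no baseline-to-6-month correlation for the ACQ; 0.30 is the only value the plan offers.
- **The trial is still informative for large effects.** With an SD of change of 1.1 and 123 per arm, power for a 0.5-point ACQ difference is about 91%. That is correct, but D.10 itself expects the group difference to be smaller than 0.5.
- **The tested contrast could be changed instead.** True, but a visit-averaged effect would be a different question from the 6-month effect and its persistence at 12 months.

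**Conclusion.** The concern holds on both counts, and the figures need correcting.

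The direction of the first error is secure under the plan's inputs: 0.29, 0.34 and 0.31 are detectable effects for a visit average, and the planned single-visit tests have less than 80% power at those values. With 123 per arm and rho 0.30, the primary 6-month figure is 51% or 37% depending on the SD used. Across the drop-out assumptions it runs from 37% to 61%, and an unstated baseline constraint raises it to at most 72% with 123 per arm. The exact size rests on equal correlation between visits, the normal approximation, and drop-out timing that the plan does not give.

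The second error needs no modelling. Under identical assumptions, a detectable effect of 0.32 at alpha 0.025 cannot exceed one of 0.31 at alpha 0.005.

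**What to change.** In D.10, remove the repeated-measures averaging, state which SD standardises the effect, and restate the figures along these lines: with 123 completers per arm and 80% power, the detectable difference in mean change from baseline at a single visit is 0.39 SD of change for Aim 1 at both 6 and 12 months (two-sided alpha 0.025), and 0.47 SD of change for the Aim 2 continuous outcomes, quality of life and FEV1 (two-sided alpha 0.005). The Aim 1 figure is about 0.43 ACQ points (0.393 × 1.1) if the WIN value of 1.1 is the SD of change. If the outcome SD is meant, give 0.47 and 0.55 at rho 0.30.

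Replace the 12-month 0.32. Say that these figures do not cover prednisone bursts, ED visits or hospitalizations, which as binary or count outcomes fall under D.9's logistic or log-linear models. If a model with equal baseline means is intended, write that into D.9 and use its figures instead (0.38 and 0.44 outcome SD at rho 0.30).

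The cost is protocol wording and less favourable detectable effects. No extra patients or procedures are needed.
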